#### Principal Investigator:

[name]

**Number and type of patients**: 62 patients with Congenital Adrenal Hyperplasia Accrual Ceiling: 62

	Number	Sex	Age Range
Patients	62	male and female	ages 2-18
Volunteers	0	V U	-

Multi-site study: No

# Précis

To test the hypothesis that the regimen of flutamide (an antiandrogen), testolactone or letrozole (an inhibitor of androgen-to-estrogen conversion), and reduced hydrocortisone dose can normalize the growth and adult stature of children with congenital adrenal hyperplasia, and can avoid the complications of supraphysiologic glucocorticoid dosage, 60 children with this disorder will be randomized to receive either the above regimen or conventional treatment until they have reached age 13 years in a girl or age 14 in a boy. After these ages boys will receive conventional treatment and girls will receive conventional treatment plus flutamide. In girls, flutamide will be continued until 6 months after menarche. All children will be followed until they have attained final adult height. The principal outcome measures will be adult height, body mass index, and bone density.

#### **Introduction**

Congenital adrenal hyperplasia (CAH) due to 21-hydroxylase deficiency is an autosomal recessive disorder involving the next-to-last enzyme of cortisol biosynthesis. The deficiency in cortisol results in an elevation of ACTH leading to adrenal hyperplasia and hypersecretion of cortisol precursors. Several of these precursors are enzymatically converted to androgens and estrogens, which cause rapid growth, premature epiphyseal fusion, and adult short stature.

CAH occurs in several clinically distinct variants that reflect differing severity of the underlying enzymatic deficiency. The most severely affected children have an inability to produce enough mineralocorticoid to prevent adrenal crisis; this is termed the salt-wasting form of CAH. The next most severely affected children can produce sufficient mineralocorticoid to avoid adrenal crisis (although they make less than the normal amount), but still produce excessive amounts of adrenal androgens from early fetal life. Girls with this variant usually have ambiguous genitalia at birth. Boys develop precocious pseudopuberty in early childhood. This form is termed simple virilizing CAH. The salt-wasting and simple virilizing forms of CAH are referred to collectively as the "classic" forms of the disorder.

Standard medical therapy for classic CAH (21-hydroxylase deficiency) has involved daily administration of glucocorticoid and mineralocorticoid. Glucocorticoid replacement suppresses ACTH secretion and thereby reduces adrenal stimulation and androgen production. However, it does not affect the intrinsic adrenal abnormality, and thus the adrenal glands continue to secrete an abnormally high ratio of androgen to cortisol at any given level of adrenal activity. Mineralocorticoid replacement suppresses plasma renin activity and angiotensin levels, and corrects the tendency of these patients to lose salt. By a mechanism still not fully understood, this helps to reduce adrenal androgen overproduction. Thus, mineralocorticoid replacement allows a lower dose of hydrocortisone to be used than would be required if glucocorticoid alone were administered.

Despite decades of study, the growth and development of most children with CAH remain abnormal [1, 2]. High levels of sex steroids induce premature epiphyseal closure; while excess glucocorticoid suppresses growth. The median adult height of treated boys was only at the 4th percentile of normal men, and the median adult height of girls, treated from before one year of age, was at the 25th percentile. Maria New and her colleagues reported adult height in all subjects that averaged 1.7 standard deviations below the mean for the normal population, which corresponds to the 9th percentile [3]. These are the results at leading clinics which pioneered hydrocortisone treatment of CAH. Moreover, retrospective studies indicate that the final height of treated patients is relatively independent of the degree of control of adrenal androgen levels, [1, 3-5] suggesting that both hyperandrogenism and hypercortisolism contributed to the observed adult short stature. A meta-analysis of data from 18 centers showed that adult heights in patients with classic CAH averaged 1.4 SD (10 cm) below the population mean [6]. A subsequent meta-analysis of 35 studies of classic CAH found the mean adult height score corrected for parental height of -1.05 standard deviation and mineralocorticoid use was associated with improved height outcome [7]. In addition, many girls encounter problems related to excess androgen despite treatment. Thus, there is need for continuing research to improve the outcome of treatment.

The suboptimal outcome of treatment is related to the theoretical inadequacy of fludrocortisone and hydrocortisone as sole treatment. If hydrocortisone is administered so as to

achieve perfectly physiologic levels, and thus perfectly normal ACTH levels and adrenal size (euplastic adrenals), the adrenals will nonetheless secrete an abnormally high ratio of androgen and estrogen to cortisol because the 21-hydroxylase deficiency shifts an excessive proportion of the steroid intermediates into the androgen and estrogen pathways. This excess androgen and estrogen will, if left unchecked, accelerate growth rate and bone maturation and compromise adult height. If, on the other hand, the hydrocortisone dose is increased above perfectly physiologic levels to control the excess androgen and estrogen production by the 21-hydroxylase-deficient adrenal glands, the resulting iatrogenic hypercortisolism will stunt growth rate, impair adult stature, decrease bone mineral density, alter intermediary metabolism, and cause hypertension. Thus, the existing approach to treatment produces either hypercortisolism, androgen excess, or a combination of these states.

Our hypothesis to improve treatment initially arose from work in the intramural program of NICHD to treat boys with familial male precocious puberty (FMPP). The accelerated growth rate and bone maturation of these boys was controlled effectively with an antiandrogen (spironolactone) and an aromatase inhibitor (testolactone) [8]. We hypothesized that a similar approach would be effective in CAH, and would allow us to avoid the complications of glucocorticoid excess by reducing hydrocortisone dose to strictly physiologic levels. An antiandrogen other than spironolactone will be required in CAH, however, since patients with CAH have a defect of the aldosterone pathway that precludes the use of spironolactone because this drug also has aldosterone antagonist activity. Thus, we have substituted flutamide for spironolactone. The aromatase inhibitor is an essential component of the regimen to prevent the maturational effects of estrogen upon bone, which are exerted at extremely low levels [9–11].

Flutamide  $(4^1$ -nitro- $3^1$  fluoromethylisobutyranilide) is a nonsteroidal antiandrogen which has been used in the treatment of prostate cancer and benign prostatic hypertrophy [12, 13]. It prevents the action of androgens by blocking the receptor sites in target tissues [14]. It may also produce changes in the metabolism of testosterone as well as estradiol [15, 16]. In comparison with other antiandrogens such as cyproterone acetate and megestrol acetate, flutamide alone has pure antiandrogenic activity, thus making it the most specific androgen antagonist for the treatment of androgen-dependent disorders [17, 18].

Testolactone has for many years been an approved drug to lower estrogen levels in women with breast cancer [19]. We have **19** years of combined experience using it in children with malelimited precocious puberty and CAH. The rationale of combined treatment of CAH with flutamide and testolactone will be to block the effects of elevated androgen levels with flutamide, and to reduce elevated estrogen levels, which are produced by peripheral conversion from the high androgen levels, with testolactone. Since these drugs act through quite different mechanisms, there is no reason to expect that their combinations will interfere with the efficacy of either drug or cause adverse effects beyond those associated with the use of these drugs individually. In fact, testolactone was found, in our studies of boys with male-limited precocious puberty, to prevent the gynecomastia that accompanied use of antiandrogen alone [8].

Both testolactone and letrozole are aromatase inhibitors. Testolactone was chosen as the drug of choice for protocol 96CH0033 years ago at a time when testolactone was being used in a variety of pediatric endocrine conditions. Over the years, other more potent aromatase inhibitors have become available. Letrozole is given once daily, while testolactone is given thrice daily. Thus,

letrozole is more convenient for the patient. Testolactone occasionally causes gastrointestinal discomfort. This side effect has been observed, but less commonly, with letrozole.

Letrozole is approved by the FDA to lower estrogen levels in adult women with breast and other cancers. Letrozole, like all aromatase inhibitors, has not been formally tested in children and has not been approved by the FDA for use in children. However, other than testolactone, letrozole is the aromatase inhibitor with the most reported pediatric experience and with the most clinical experience by investigators at the Clinical Center. Letrozole was used at the Clinical Center in the treatment of children with McCune Albright syndrome (protocol 00-D-0183). In this protocol, girls with precocious puberty and McCune Albright syndrome experienced an improvement in their puberty without any apparent harmful side-effects[20]. Moreover, pediatric endocrinologists have used letrozole to treat other endocrine conditions in children[21]. Safe and effective use of letrozole in children has been reported for the treatment of idiopathic short stature [22, 23]; and in combination with testosterone for male pubertal delay [24–26].

Continuation of flutamide therapy during puberty has the advantage of possibly protecting the ovaries against the development of polycystic ovarian syndrome (PCOS). Fertility in females with CAH is an ultimate and attainable goal. Delay of the average age of menarche in girls with classic CAH has been reported from various clinics [2, 27]. Menstrual irregularities, anovulation, infertility in females with CAH is not always due to the undertreated state of hyperandrogenism. CAH females have been found to have increased adrenal progesterone secretion [28], as well as elevated estrogen of adrenal origin [27]. A PCO-syndrome type of ovarian dysfunction has been described in women with CAH [29]. Androgens may directly prevent the maturation of follicles and/or affect the hypothalamic-pituitary-gonadal axis, which then induces morphologic and biochemical changes characteristic of polycystic ovarian syndrome. Ovarian dysfunction in females with CAH may be due to an abnormality either at the hypothalamic, pituitary or ovarian level, and inadequate control of excessive adrenal sex steroids (androgens, progestins, estrogens alone or in combination) may contribute to menstrual and reproductive disorders in CAH females. We hypothesize that flutamide treatment during puberty will antagonize intraovarian levels of androgens, normalize the age of onset of menarche and reduce the incidence of PCOS. The use of flutamide will also allow for a lower glucocorticoid dose.

We completed a pilot study which consisted of a 6-month trial of flutamide plus testolactone, added to a modified conventional regimen (modified by restricting hydrocortisone dosage to a physiologic level), compared to conventional treatment with hydrocortisone plus fludrocortisone [30]. The sequence of 6-month periods was chosen randomly with a 3-month "washout" period between each 6-month arm.

Results from this pilot study revealed that the rate of growth, weight gain, and bone maturation normalized with treatment with flutamide, testolactone and low dose hydrocortisone. No significant adverse effects were observed. Because a 6-month treatment period was too short to provide meaningful assessment of the effects of flutamide and testolactone on long-term growth rate, bone age advancement, and predicted adult height, a 2-year trial of flutamide plus testolactone, added to the modified conventional regimen of hydrocortisone and fludrocortisone was undertaken. Children were randomized to receive either conventional treatment or the investigational regimen of flutamide, testolactone, and reduced hydrocortisone dose. An open design was employed because the hydrocortisone dosage adjustments required during conventional treatment would have made it very difficult to carry out a blind study. Results from this 2-year study show that there is continued normalization of the rate of growth, weight gain, and bone age maturation, without any significant adverse side effects [31]. Based upon these findings, we have decided to conduct a long-term trial to test the hypothesis that this new regimen can normalize the growth and development of children with CAH.

### Evaluation of the Project in Relation to Criteria for NICHD Clinical Protocols

(1) The protocol addresses fundamental aspects of human physiology or pathophysiology.

The protocol addresses four fundamental issues related to the pathophysiology of congenital adrenal hyperplasia and its impact on growth and development. First, it tests the hypothesis that some of the undesired outcomes of conventionally treated patients, such as obesity, are due to glucocorticoid excess, and that these undesired outcomes can be avoided by reduction of the glucocorticoid dose to physiologic levels [32, 33]. To our knowledge the current trial is the only long-term randomized study of CAH that involves the restriction of hydrocortisone dose to a strictly physiologic level. Second, the protocol examines the hypothesis that estrogen contributes to the impaired adult height in CAH by using an inhibitor of estrogen synthesis. This hypothesis is in accord with the observation of delayed epiphyseal fusion and tall stature in individuals with a defect in the estrogen receptor [11] or in the estrogen biosynthetic enzyme aromatase [34]. To our knowledge, the current study is the only long-term randomized trial of an aromatase inhibitor in any of the LHRH-independent forms of precocious puberty. Lastly, the protocol addresses the hypotheses that early exposure to androgens influences the developing brain and ovaries and has an effect on cognition and reproductive function in females.

(2) The protocol outcome has a reasonable potential to impact significantly on the public health.

Congenital adrenal hyperplasia occurs in only 1 in 15,000 individuals. Thus, even the complete elimination of the disorder would have at best a minimal impact on the public health. No study of a new treatment regimen for congenital adrenal hyperplasia can be expected to meet the above criterion because the disorder is so rare.

Ancillary studies of the population of children with CAH followed in this protocol have the potential to impact significantly on public health. Extending our studies to the pubertal period in girls with CAH may provide insight into the long-term consequences of early ovarian exposure to androgens. PCO affects 7% of women of reproductive age and is a significant public health issue. The effects of extraovarian sources of androgens (i.e. adrenal) on the development of PCO is not well understood. Moreover, the protocol includes behavioral and cognitive testing which may provide insight into how hormones affect behavior and the developmental consequences of early exposure to androgens. Learning disabilities are a significant public health issue and are much more common in boys than girls. Studies of children with CAH may provide insight into hormonal influences in the development of learning disabilities.

(3) The protocol represents research in the diagnosis or treatment of orphan or rare diseases that is relatively unlikely to be performed outside the Clinical Center.

Congenital adrenal hyperplasia is indeed an orphan or rare disease. During a recent literature review, we failed to find a single study, even a short-term study, in which two or more therapies

had been subjected to a randomized trial. However, there is widespread recognition among the pediatric endocrine community of the need for improved treatments of this disorder. The Clinical Center is uniquely suited to overcome the principal obstacles to a long-term study of this sort, namely, (1) recruitment of patients, (2) successful long-term follow-up, and (3) stable funding over the long duration of the project.

(4) The responsible and principal investigators have clinical training and expertise appropriate for supervising the care of patients on the protocol and the study design is adequate.

The principal investigator,				
			-	
			81	
Associate investigator,	8 308 8 M	i 6 6	1. 1. 11.	
-				

The study design is similar to that of other NICHD long-term trials (83-CH-199, 87-CH-152, 91-CH-46) in which adult height is a principal outcome measure. The difference in the design of the current study is the absence of a double-blind design. This difference reflects the complexity of CAH treatment, and the need to adjust hydrocortisone dose in the conventional treatment arm but not in the investigational treatment arm. Thus, the decision to choose an open rather than double-blind design reflected our judgement that a double-blind design would be unworkable.

(5) The protocol can only be carried out at the NIH, or can be carried out more effectively and efficiently by intramural than extramural investigators.

As indicated in item 3 above, the intramural program has significant advantages for conducting this protocol due to its ability to recruit an adequate number of subjects with a rare disease, its low drop-out rate in long-term trials, and the availability of stable long-term funding.

(6) The protocol has a favorable cost-benefit ratio.

The ultimate implication of the study for the cost of CAH treatment is difficult to assess for two reasons. First, the effectiveness of aromatase inhibitors for treatment of breast cancer, and of antiandrogens for treatment of prostate cancer, has led to intense pharmaceutical company interest in these drug classes. Several highly promising drugs that cannot now be used in children are under development. By the time the current study can determine whether or not the regimen of antiandrogen and aromatase inhibitor offers long-term benefit, there will probably be alternative drugs available in each class that will have greater potency, fewer side effects, and perhaps lower cost. Second, although the cost of drugs for the investigational regimen always exceeds that for conventional treatment (because of the two additional drugs), the cost of monitoring will be less. This is due to the reduced need to monitor androgen levels when they are being blocked by an antiandrogen. Since the cost of monitoring multiple steroid levels at 3-6 month intervals throughout childhood can be quite high, the increased drug cost may be offset by reduced monitoring cost. Our prediction is that the cost-benefit ratio for the investigational approach will be favorable if the long-term benefits that we hypothesize are in fact achieved.

### Study objectives and endpoints

Success in normalizing adult height is a sensitive measure of control of excess sex steroid action and avoidance of excess glucocorticoid action during childhood.

### **Primary** objective

 To demonstrate the superior efficacy of the combination regimen of an antiandrogen, aromatase inhibitor and reduced hydrocortisone dose compared with standard glucocorticoid replacement therapy in achieving taller adult stature in classic congenital adrenal hyperplasia.

### Secondary Objectives

- To assess the safety and tolerability of antiandrogen, aromatase inhibitor and reduced hydrocortisone dose combination therapy.
- To assess the effect of antiandrogen, aromatase inhibitor and reduced hydrocortisone dose combination therapy on height gain, growth velocity and bone maturation prior to puberty.
- To assess the effect of antiandrogen, aromatase inhibitor and reduced hydrocortisone dose combination therapy on height gain and bone maturation during puberty
- To assess the effect of antiandrogen, aromatase inhibitor and reduced hydrocortisone dose combination therapy on development of TART in males and establishment of menstrual regularity in females
- To assess the effect of antiandrogen, aromatase inhibitor and reduced hydrocortisone dose combination therapy on fasting glucose, body mass index, and bone mineral density
- To assess hormonal control based on percent of visits within the normal (or optimal) range for 17OHP, androstenedione, PRA and ACTH
- To assess sex differences in outcomes.

## A. Primary Endpoint

The operational definition of attainment of adult height was defined as the study visit at which the incremental growth declined <1.5 cm (0.6 inch) over 12 months.

The primary outcome variable is adult height which will be expressed in SD units relative to the normal population.

# **B** Secondary Endpoints

Secondary outcome variables will be examined between the two study arms at baseline, pubertal onset and adult height (final visit). To examine sex differences, the secondary outcomes variables will be examined by-sex between the two study arms.

'Pubertal Onset' is defined as the visit when patients entered puberty (Tanner 2 breast in females, testicle size > 3mL) or completed therapy with the aromatase inhibitor and or LHRHa.

- i. Adult height achieved will also be expressed standard deviation (SD) units and in cm as the difference in height achieved in relation to their target height (i.e., mid-parental height, calculated based on their parental heights)
- ii. Height achieved (SD units) from baseline to pubertal onset
- iii. Height achieved (SD units) from pubertal onset to adult height
- iv. Predicted adult height (using Bayley-Pinneau method) at pubertal onset
- v. Predicted adult height (using Bayley-Pinneau method) change from baseline to pubertal onset
- vi. Predicted adult height (using Bayley-Pinneau method) change from pubertal onset to final height
- vii. Growth velocity (in SD units) from baseline to pubertal onset
- viii. Growth velocity (in SD units) from pubertal onset to adult height
- ix. Percent of visits with ACTH in normal range from baseline to pubertal onset
- x. Percent of visits with ACTH in normal range from pubertal onset to adult height
- xi. Percent of visits with androstenedione in normal range from baseline to pubertal onset
- xii. Percent of visits with androstenedione in normal range from pubertal onset to adult height
- xiii. Percent of visits with 17-hydroxyprogesterone in the optimal range (<1,200 ng/dL) or high (>1,200 ng/dL) from baseline to pubertal onset
- xiv. Percent of visits with 17-hydroxyprogesterone in the in the optimal range (<1,200 ng/dL) or high (>1,200 ng/dL) from pubertal onset to adult height
- xv. Percent of patients with onset of central precocious puberty (CPP)
- xvi. Rate of bone maturation as change in bone age from baseline to pubertal onset / change in chronological age from baseline to pubertal onset; change in bone age from pubertal onset to adult height / change in chronological age from pubertal onset to adult height; change in bone age from baseline to adult height / change in chronological age from baseline to adult height. Bone age assessment will be performed manually using Greulich and Pyle atlas method and by automated software (BoneXpert) in a subset of patients visit who have availability of digital bone age images.

xvii. Number of years bone age remain unchanged from baseline to pubertal onset

xviii. Dose of hydrocortisone at baseline, pubertal onset and adult height, baseline to pubertal and pubertal to adult height

xix. Cumulative glucocorticoid exposure over time

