#### Analysis of Study (please also see attached SAP Appendix A)

- The primary outcome (adult height expressed in SD units) will be compared between groups at the conclusion of the study using the unpaired two-tailed Student's t-test, or nonparametric Wilcoxon rank sum test, as appropriate
- Secondary outcome measures during the study include hormone levels (percent of visits in ranged defined above) and treatment doses, BMI (as SD units), final BMD (Z-score), growth velocity (in SD units), rate of bone maturation, and predicted adult height (Bayley-Pinneau method, automated software in a subset of patients) at baseline, pubertal onset, and final visit. These outcomes will be compared between the study arms by multivariable mixed models for repeated measures. These models will allow for within-subject comparisons between timepoints, as well as account for their correlations across time, adjust for potential confounders, and specify the appropriate outcome distribution (e.g., normal, binomial, or Poisson distribution for type of data). They are a robust method for accommodating missing data, especially in measures that are repeated and collected longitudinally. Post-hoc comparisons will identify the driving factors and group effect influencing any observed differences, and will be corrected for multiple comparisons as applicable.

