We have chosen a group size of 30, giving this study the same statistical power as the study of Deslorelin-induced pubertal delay (83-CH-199). With an expected standard deviation of 6 cm for the final height measurements (approximately that of the normal population), the group size required to give a 80% power to detect a 5-cm difference (about 2 inches) at a p<0.05 is 24. The group size needed to detect a 6-cm difference is 17. This is regarded by the pediatric endocrine community as a reasonable power for a growth study - for example, the Genentech Collaborative Study of Turner Syndrome had a group size of 17. Thus, the study is designed to detect at least a 5 cm difference in final height, a clinically meaningful difference, and allows for a 25% drop out rate over the course of the study. This is regarded by the pediatric endocrine community as a reasonable power for example, the Genentech Collaborative Study of Turner Syndrome had a group size of 17. Thus, the study is designed to detect at least a 5 cm difference in final height, a clinically meaningful difference, and allows for a 25% drop out rate over the course of the study - for example, the Genentech Collaborative Study of Turner Syndrome had a group size of 17. Thus, the study is designed to detect at least a 5 cm difference in final height, a clinically end by the pediatric endocrine community as a reasonable power for a growth study - for example, the Genentech Collaborative Study of Turner Syndrome had a group size of 17. Thus, the study is designed to detect at least a 5 cm difference in final height, a clinically meaningful difference, and allows for a 25% drop out rate over the Degree **19** of **26** 

Abbreviated Title: Congenital Adrenal Hyperplasia Version Date: 03/23/2023

course of the study.

Please find attached study analysis plan.

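### Sex differences are a secondary objective, but the supplied text plans only arm comparisons within each sex and names no arm-by-sex contrast

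*Combined protocol and SAP*

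**What the plan says.** The Secondary Objectives include "To assess sex differences in outcomes". The section on Secondary Endpoints states how: "To examine sex differences, the secondary outcomes variables will be examined by-sex between the two study arms". That sentence covers secondary variables only.

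Under Analysis of Study, the secondary measures get a model: "These outcomes will be compared between the study arms by multivariable mixed models for repeated measures". The models are to adjust for possible confounders, which are not listed. A follow-up step is described in general terms: "Post-hoc comparisons will identify the driving factors and group effect influencing any observed differences", and these comparisons "will be corrected for multiple comparisons as applicable". Sex is not named as a factor, and no arm-by-sex term or contrast appears. The section heading refers the reader onward ("please also see attached SAP Appendix A"), but the text of that appendix is not among the supplied documents.

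**The concern.** A sex difference in the treatment effect is a difference between two arm effects, one in girls and one in boys. Examining the arms within each sex gives the two effects. It does not estimate or test the gap between them unless they are set against each other. Adjusting for sex as a confounder does not help either, because that gives one common arm effect.

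The documents do not say that significance in one sex will be taken as a sex difference. But the supplied text promises no other result for this objective, so a reader would be left to compare two within-sex results by eye.

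The question is a real one here. Under the Précis and the Protocol section, boys on the investigational regimen return to conventional treatment at about age 14, while girls stop the aromatase inhibitor at about 13 and continue flutamide. Effects on the endpoints from pubertal onset to adult height could plausibly differ by sex.

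**Working it through.** **Inputs.** From Analysis of Study: a 5 cm difference, two-sided 0.05, 24 per arm required, 30 per arm chosen, and the SD ("With an expected standard deviation of 6 cm for the final height measurements"). Assumption: equal numbers of boys and girls, since the documents give no numbers per sex. Let n be patients per arm per sex: n = 12 (half of 24) or n = 15 (half of 30).

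**The plan's own figures.** An exact two-sided two-sample t-test at SD 6 cm needs 23.6, so 24 per arm, for 5 cm, and 16.7, so 17 per arm, for 6 cm. Power is 80.7% in both cases. Both stated sizes reproduce.

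**Power within one sex.** SE = 6·√(2/n), df = 2n − 2, noncentral t:
- n = 12: SE = 2.45 cm, power for 5 cm p = 0.497
- n = 15: SE = 2.19 cm, p = 0.596

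**Chance that exactly one sex is significant** (uncorrected):
- Same 5 cm effect in both sexes: 2p(1 − p) = 2 × 0.497 × 0.503 = 0.50 (n = 12); 0.48 (n = 15)
- 5 cm in one sex, none in the other: 0.95p + 0.05(1 − p) = 0.472 + 0.025 = 0.50 (n = 12); 0.59 (n = 15)

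At these inputs the one-sex pattern is about as likely with no sex difference as with a 5 cm one.

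**Where the pattern does discriminate.** Both sexes are significant in p² = 25% of trials under equal effects, against 0.05p = 2.5% under 5 v 0 cm (n = 12); for n = 15, 36% against 3.0%. A 10 v 0 cm effect gives one-sex significance in 93% (n = 12) or 94% (n = 15). The SD matters a good deal:

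| SD (cm) | n = 12: equal effect | n = 12: 5 v 0 cm | n = 15: equal effect | n = 15: 5 v 0 cm |
|---|---|---|---|---|
| 7 | 47% | 40% | 50% | 47% |
| 6 | 50% | 50% | 48% | 59% |
| 5 | 46% | 63% | 37% | 73% |
| 4 | 28% | 80% | 16% | 87% |

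**Other sensitivities, equal 5 cm effect, SD 6 cm.** An unequal sex split of 10/14 or 8/16 per arm gives one-sex significance in 51% or 54%. Bonferroni over the two sexes gives 47% (n = 12) or 50% (n = 15). Bonferroni over 19 endpoints, an assumed reading of the correction clause, gives 21% or 30%.

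**The direct contrast.** SE = SD·√(4/n), df = 4n − 4. At n = 12 and SD 6 cm the SE is 3.46 cm, twice the 1.73 cm (6·√(2/24)) for the overall arm effect.

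| | n = 12 | n = 15 |
|---|---|---|
| 95% CI half-width, SD 6 cm | 6.98 cm | 6.21 cm |
| Power, 5 cm difference in effect, SD 6 cm | 29% | 35% |
| Power, 10 cm difference in effect, SD 6 cm | 81% | 89% |
| 95% CI half-width, SD 4 cm | 4.65 cm | 4.14 cm |
| Power, 5 cm difference in effect, SD 4 cm | 56% | 66% |

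In simulation (200,000 replicates, SD 6 cm) its type I error is 5%. Among trials with exactly one sex significant at n = 12, the contrast is significant in 10% under an equal effect, 50% under 5 v 0 cm and 83% under 10 v 0 cm. It separates cases that the one-sex pattern does not.

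**The case against.** The strongest reply is that model terms belong in SAP Appendix A, which is not in the supplied text, and that the by-sex sentence is a loose remark in an endpoint list. The planned models could carry an arm-by-sex term. This stands as a limit: the point is that none is named in what was supplied, not that none exists. If the appendix has the term, the Secondary Endpoints wording still describes something else and should be aligned.

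Second, no document states the one-sex-significant rule that the calculations examine, and boys and girls are independent groups, so two reported effects with standard errors give the contrast by subtraction. That is correct, but the text does not promise those estimates and leaves the comparison to the reader.

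Third, the numbers are borrowed from adult height. The by-sex sentence covers secondary variables, of which only the first is close: height relative to parental target, expressed in SD units and also "in cm as the difference in height achieved in relation to their target height", with no SD given. No effect sizes are given for the others. At SD 4 cm the one-sex pattern is informative. All this stands; the missing contrast does not depend on the illustration.

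Fourth, after age 13 or 14 the regimens differ by sex, so a contrast on later endpoints cannot isolate sex from treatment. That also stands, but it applies equally to the within-sex results. The contrast still compares the assigned strategies between the sexes.

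Finally, power is low. That argues for an estimate with an interval, which shows the uncertainty, over a pair of within-sex p-values, which hides it.

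**Conclusion.** The concern holds. In the supplied text, a named secondary objective has no analysis that estimates or tests it. At the adult-height design values with an equal sex split, one-sex significance occurs in about half of trials under an equal effect (50% at 12 per arm per sex, 48% at 15), and in 50% or 59% when only one sex gains 5 cm.

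The size rests on the 6 cm SD, the 5 cm effect, the assumed sex split and no multiplicity correction; it shrinks at smaller SDs and transfers only approximately to other endpoints. The conclusion is limited by the unseen Appendix A. It touches one secondary objective and leaves the primary analysis alone. The change should be made.

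**What to change.** - Add sex and an arm-by-sex term to the planned mixed models. Where a model has several time points, include the time interactions needed to read the contrast at each named one.
- State the scale of the contrast (difference or ratio) for binomial and Poisson outcomes.
- Base any statement about sex differences on that contrast and its 95% CI. Report the within-sex arm differences from the same model, with intervals, as descriptive.
- For endpoints after age 13 or 14, say that the contrast compares assigned strategies by sex and does not isolate sex itself.
- Bring the Secondary Endpoints section, Analysis of Study and SAP Appendix A into line, and say whether the multiplicity correction covers these contrasts.

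The cost is model terms and wording; no new data are needed. The downside is precision: 80% power at SD 6 cm needs a difference in effect of about 9.9 cm (12 per cell) or 8.8 cm (15 per cell), and detecting 5 cm would take about 46 per cell, 4 × 46 = 184 patients. Sparse binary outcomes, such as onset of central precocious puberty, may give unstable interaction estimates. The plan should say that a non-significant contrast will not be reported as absence of a sex difference.
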